After the second interim analysis (80% planned enrollment through Protocol Amendment 4), in order to improve estimation precision of the treatment effect in the clinically relevant key secondary endpoint of COVID-19-related hospitalization or death from any cause, the sample size was adjusted to approximately 1880 participants. This adjustment is expected to provide the required total number of 26 COVID-19-related hospitalizations or death from any cause, which will have approximately 90% conditional power (based on the second interim analysis data) such that the nominal 95% CI of the treatment group difference in the event rate does not include 0 when assuming that PF-07321332/ritonavir reduces the event rate by 70% or more relative to placebo.

[figure not shown]
The sample size increase of 740 participants is based on the assumption of a 1.5% event rate for the targeted enrollment countries. The number of participants is approximately 1880 (1140 enrolled participants plus the increase of 740 participants). Assuming a 5% premature study discontinuation rate, approximately 1980 participants will be enrolled in the study.

A third interim analysis (100% planned enrollment through Protocol Amendment 4) to support regulatory filings was performed utilizing the dataset from 19 December 2021, which includes participants who had risk factors for severe COVID-19 illness and who were vaccinated against the SARS-CoV-2 virus as well as participants who did not have risk factors for severe COVID-19 illness and who were not vaccinated. This dataset was originally prepared to support an analysis based on all participants enrolled prior to Protocol Amendment 5 (21 January 2022). The data were never released nor analyzed previously because the protocol was amended (Protocol Amendment 5) to increase the sample size. Alpha was adjusted for the first interim analysis (45% planned enrollment through Protocol Amendment 4), no further adjustment for alpha was performed in the second interim analysis (80% planned enrollment through Protocol Amendment 4) and no adjustment for alpha was performed in the the third interim analysis (100% planned enrollment through Protocol Amendment 4). At the first interim analysis (45%), the IA met futility criteria and there is no remaining alpha for subsequent hypothesis tests. Thus all further analysis will use nominal p-values for reporting.

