9.1. Statistical Hypotheses

The primary hypothesis to be tested is whether or not there is a difference in median time (days) to sustained alleviation of all targeted COVID-19 signs and symptoms through Day 28 between PF-07321332/ritonavir and placebo. The statistical hypothesis is as follows:

- The null hypothesis (H_0) is that there is no difference in median time to sustained alleviation of targeted symptoms of COVID-19 between PF-07321332/ritonavir and placebo;
- The alternative hypothesis (H_1) is that there is a difference in median time to sustained alleviation of targeted symptoms of COVID-19 between PF-07321332/ritonavir and placebo.

Because the prespecified 45% interim analysis of the primary endpoint was not met, the following secondary endpoints will be analyzed to provide a point estimate and 95% CI to measure associated variability. The analysis will be performed with a nominal alpha:

- 1) Proportion of participants with COVID-19-related hospitalization or death from any cause through Day 28.
- 2) Number of COVID-19-related medical visits through Day 28.

In support of the COVID-19 related medical visits endpoint, the number of days in hospital and ICU stay in patients with COVID-19-related hospitalization through Day 28 will be summarized.

Other secondary endpoints, which will be identified in the SAP, will be subsequently tested following the Hochberg procedure.⁴¹

Imputation of missing data within other specific efficacy variables and endpoints will be computed according to the rules specified in the SAP.

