9.3.1. General Considerations

Descriptive statistics for all efficacy endpoints by treatment group and visit will be provided.

The number of participants screened will be reported. The number of participants randomized to the double-blind treatment phase, completing the study drug administration, completing the study, and discontinued the study will be summarized from the FAS analysis set for each treatment group.

Baseline demographic and other characteristics will be tabulated for the FAS analysis set and summarized by treatment group. Quantitative variables will be described by standard descriptive statistics (mean, standard deviation, minimum, and maximum), and qualitative variables will be summarized by frequency tables with number and proportion in each category (with the corresponding sample sizes).

For continuous endpoints, MMRM analysis of covariance model will be used to analyze change from baseline over time. Estimated mean differences between treatments and their respective 95% CI and p-values will be calculated.

Binary endpoints will be summarized with the number and percent of participants satisfying the endpoint. Comparisons between groups will be presented as odds ratios with 95% confidence intervals based on logistic regression analysis with terms for treatment.

For categorical endpoints, proportion of participant for each category will be summarized for each group.

For count endpoints, the total number of the events and average number of events will be summarized for each group.

Time-to-event endpoints will be summarized with Kaplan-Meier curves. Log-rank test will be used to compare the median time-to-event between the treatment group. Rate ratios or hazard ratios and the associated 95% 2-sided CIs will be estimated by Cox proportional hazards models, including treatment and the strata as covariate.

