5.1. Hypotheses and Decision Rules

The primary hypothesis to be tested is whether or not there is a difference in median time (days) to sustained alleviation of all targeted COVID-19 signs and symptoms through Day 28 between PF-07321332/ritonavir and placebo. The statistical hypothesis is as follows:

- *The null hypothesis (H₀) is that there is no difference in median time to sustained alleviation of targeted symptoms of COVID-19 between PF-07321332/ritonavir and placebo.*
- *The alternative hypothesis (H₁) is that there is a difference in median time to sustained alleviation of targeted symptoms of COVID-19 between PF-07321332/ritonavir and placebo.*

Because the prespecified 45% interim analysis of the primary endpoint was not met, the following secondary endpoints will be analyzed to provide a point estimate and 95% CI to measure associated variability. The analysis will be performed with a nominal alpha:

- 1) Proportion of participants with COVID-19-related hospitalization or death from any cause through Day 28.*
- 2) Number of COVID-19-related medical visits through Day 28.*

In support of the COVID-19 related medical visits endpoint, the number of days in hospital and ICU stay in patients with COVID-19-related hospitalization through Day 28 will be summarized.

Other secondary endpoints listed below will be subsequently tested following the Hochberg procedure.

- Time (days) to sustained resolution of all targeted signs/symptoms through Day 28 mITT1 population.
- Proportion of participants with a resting peripheral oxygen saturation $\geq 95\%$ at Days 1 and 5 mITT1 population.
- Proportion of participants with severe signs/symptoms attributed to COVID 19 through Day 28.

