5.2.1. Analyses for Binary Endpoints

Binary endpoints other than COVID-19 related hospitalization and death due to any cause (ie, proportion of participants with severe signs/symptoms attributed to COVID-19 through Day 28, worsening status in 1 or more self-reported COVID-19 associated symptoms through Day 28 and proportion of participants with death [all cause] through Week 24) will be summarized with the number and percent of participants satisfying the endpoint. Treatment comparisons between groups will be presented as odds ratios with 95% confidence intervals and P-value based on logistic regression model (if data permits).

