5.2.3. Analyses for Categorical Endpoints

For categorical endpoints, (ie, proportion of participants with a resting peripheral oxygen saturation $\geq 95\%$ at Days 1 and 5), proportion of participants for each category will be summarized for each group and a test for homogeneity of odds ratio using Breslow-Day test will be summarized.

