worsening will be assessed to include hospitalization due to COVID-19 and death of any cause. An expanded definition of worsening of signs and symptoms that will include CRF data (hospitalization due to COVID-19 and death of any cause) is defined as follows: Participant with hospitalization due COVID-19 or death of any cause will be considered as having worse signs and symptoms, this definition overrides the observed worsening of signs and symptoms from participant diary data. To incorporate hospitalization and death in the expanded worsening of signs and symptoms, date of hospitalization and date of discharge will be used.

To evaluate the progression to worsening of symptoms attributed to COVID-19, the following analysis will be performed for both worsening and expanded worsening and treatment comparison between groups will be done using the same statistical method as mentioned above:

- Proportion of participants with any progression to worsening of targeted symptoms attributed to COVID-19 Day 2 to Day 6 (during treatment).
- Proportion of participants with any progression to worsening of targeted symptoms attributed to COVID-19 Day 7 to Day 28 (post treatment).

6.2.11. Proportion of Participants with a Resting Peripheral Oxygen Saturation $\geq 95\%$ at Days 1 and 5

The oxygen saturation level will be measured for each participant. A resting peripheral oxygen saturation will be derived programmatically based on following table:

Oxygen saturation (Yes/No)	
$\geq 95\%$	Yes
$< 95\%$	No

The count and proportion of participants with a resting peripheral oxygen saturation $\geq 95\%$ will be summarized by treatment group and by visits (Days 1 and 5). A cross tabulation will be presented for both Day 1 and Day 5, ie, for each proportion presented at Day 1, both proportions at Day 5 will be summarized. Treatment comparison between group for the odds ratio (baseline (Day 1) $\geq 95\%$ vs $< 95\%$) of comparing oxygen saturation $\geq 95\%$ at Day 5 will be analyzed with a Breslow-Day test for homogeneity of the odds ratios. The analyses will be done using mITT1 populations. Missing data at Day 1 or Day 5 will be excluded from the analysis.

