Progression to a expanded worsening status in 1 or more self-reported COVID19 associated symptoms through Day 28.	Secondary analysis	mITT1	All data collected will be included regardless of intercurrent events. Missing severity at baseline will be treated as mild.	Logistic regression model
Proportion of participants with a resting peripheral oxygen saturation $\geq 95\%$ at Days 1 and 5.	Secondary analysis	mITT1	All data collected will be included regardless of intercurrent events. Missing data will not be imputed.	Breslow-Day test for Homogeneity of the Odds Ratios
Viral titers measured via RT-PCR in nasal swabs over time.	Secondary analysis	mITT1	All data collected will be included regardless of intercurrent events. If visit data in viral load is missing, the earliest measurement	MMRM analysis

Endpoint	Analysis Type	Population	Data Inclusion and Rules for Handling Intercurrent Events and Missing Data	Analysis Model
			closest to the visit will be used for the visit.	
Viral titers measured via RTPCR in nasopharyngeal samples at Day 1 and Day 5.	Sensitivity analysis (POC)	mITT1	All data collected will be included regardless of intercurrent events. Use baseline viral load (continuous).	ANCOVA analysis
CCI [REDACTED]	CCI [REDACTED]	CCI [REDACTED]	CCI [REDACTED]	CCI [REDACTED]

* All: Combining mITT1 population from before and after Protocol Amendment #6, dated 09 Jun 2022.

Pre-PA5: mITT1 population from before Protocol Amendment #5, dated 21 Jan 2022,

Post-PA5: mITT1 population from after Protocol Amendment #5, dated 21 Jan 2022

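### The between-arm test planned for Day-5 oxygen saturation (Breslow-Day) tests an interaction, so no treatment effect is estimated or tested

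*SAP*

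**What the plan says.** SAP 6.2.11 derives SpO2 as Yes/No at a 95% cut-off. It reports counts and proportions by arm and visit, cross-tabulates Day 1 against Day 5, and excludes participants with either value missing. The between-arm comparison of SpO2 ≥95% "at Day 5 will be analyzed with a Breslow-Day test for homogeneity of the odds ratios".

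SAP 5.2.3 classes the endpoint as categorical. Beyond proportions it plans only that "a test for homogeneity of odds ratio using Breslow-Day test will be summarized". The analysis-model column of Appendix 1 reads "Breslow-Day test for Homogeneity of the Odds Ratios".

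Protocol 9.3.1 says of binary endpoints: "Comparisons between groups will be presented as odds ratios with 95% confidence intervals based on logistic regression analysis with terms for treatment". SAP 5.2.1 carries that rule over for severe symptoms, worsening status and all-cause death through Week 24, but SpO2 is not in its list.

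The endpoint serves a comparative objective (protocol section 3). It is also one of three endpoints in SAP 5.1 of which the plan says: "Other secondary endpoints listed below will be subsequently tested following the Hochberg procedure".

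**The concern.** The plan labels this analysis a treatment comparison, but the null hypothesis of a Breslow-Day test is that an odds ratio is the same in every stratum. A drug that improves the odds of a good Day-5 value equally for everyone satisfies that null exactly.

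The one p-value produced would therefore answer a different question from the objective. A large value could be read as no treatment effect, and a small one as benefit, when the test gives neither direction nor size. No effect estimate or interval is planned to correct either reading. If the Hochberg step in SAP 5.1 is carried out, an interaction p-value would also enter a family whose other members are treatment comparisons.

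**Working it through.** **What the test examines.** The SAP sentence can be read in two ways.

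- Strata are the Day-1 groups: compare OR(treatment | Day-1 ≥95%) with OR(treatment | Day-1 <95%).
- Strata are the arms: compare OR(Day 1 vs Day 5 | active) with OR(Day 1 vs Day 5 | placebo).

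The data are one 2×2×2 table, and the ratio of the two odds ratios is the same number in both readings. Both test the three-way interaction.

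**Inputs.** The documents give no SpO2 rates and no power figure for this endpoint, so there is nothing to reproduce. The SAP 2.3 total of 1880 at 1:1 gives 1880/2 = 940 per arm. All rates below are assumptions, and every participant is taken as evaluable.

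**Worked example with expected counts.** Assume 90% have Day-1 ≥95% (846 per arm, leaving 94), placebo Day-5 rates of 92% and 60%, and a treatment odds ratio of 2 in both groups.

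- Day-1 ≥95%: placebo odds 0.92/0.08 = 11.5; active odds 23, rate 23/24 = 95.8%.
- Day-1 <95%: placebo odds 0.60/0.40 = 1.5; active odds 3, rate 3/4 = 75%.

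| Day-1 group | Active yes / no | Placebo yes / no | Treatment OR |
|---|---|---|---|
| ≥95% | 810.75 / 35.25 | 778.32 / 67.68 | 2.00 |
| <95% | 70.5 / 23.5 | 56.4 / 37.6 | 2.00 |

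Overall Day-5 rates are (810.75 + 70.5)/940 = 93.8% and (778.32 + 56.4)/940 = 88.8%.

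- Breslow-Day, strata = Day-1 group: 2.00 vs 2.00, p = 1.00.
- Breslow-Day, strata = arm: 23/3 = 7.67 vs 11.5/1.5 = 7.67, p = 1.00.
- CMH stratified by Day-1 group: observed minus expected is 16.215 + 7.05 = 23.265; variance is 24.18 + 10.37 = 34.55; chi-square is 23.265²/34.55 = 15.67, p = 0.00008. The pooled odds ratio is 2.00 (95% CI 1.41 to 2.83).

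A five-point difference that a treatment test detects clearly is invisible to the planned test.

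**Simulation.** There were 10,000 trials in each of 8 rate sets: Day-1 ≥95% in 90% or 95%; placebo Day-5 rate 90% or 95% if Day-1 ≥95%, and 50% or 60% if Day-1 <95%. Tests were two-sided at 5%, with no Tarone adjustment for Breslow-Day and no continuity correction for CMH. Ranges are minimum to maximum over the rate sets; the Breslow-Day range covers both readings.

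| Scenario | Breslow-Day rejects | CMH rejects |
|---|---|---|
| Common OR 1.5 | 4.9–5.4% | 49–77% |
| Common OR 2 | 4.9–5.5% | 88–99% |
| Common OR 3 | 4.7–5.4% | 99.6–100% |
| +2 points in both groups | 6–22% | 28–51% |
| +3 points in both groups | 9–52% | 55–88% |
| +4 points in both groups | 13–91% | 82–99.6% |
| No net change (+15 points if Day-1 <95%, offset if ≥95%) | 34–75% | 5% |

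In the last row the offsetting loss is small: 15 × 0.10/0.90 = 1.7 points, or 15 × 0.05/0.95 = 0.8 points.

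A second set of runs used 570 or 940 per arm, 80% to 95% with Day-1 ≥95%, and the worked example's placebo rates. For odds ratios 1.5 to 3, Breslow-Day rejected in 4.1–6.2% and CMH in 44–100%. With an odds ratio of 3 in the low group and 0.8 in the high group (940 per arm, 90% high), Breslow-Day rejected in 95% and CMH in 6%.

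**The case against.** **The SAP may depart from the protocol.** Section 9 lets it modify methods where appropriate, and protocol 9.3.3 specifically leaves the SpO2 analysis to it. Protocol 9.3.1 also has a separate rule for categorical endpoints that asks only for proportions, and SAP 5.2.3 uses that class. This stands in part: it is not a bare breach of the protocol. But the endpoint is Yes/No, SAP 6.2.10 gives an endpoint derived in the same way a logistic model, and no reason is offered for the difference. The label does not turn Breslow-Day into a treatment test.

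**The question is defined.** Whether the Day 1 to Day 5 association differs by arm can be asked. It can, but it is not the comparison that the objective or the SAP's own label promises.

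**Little depends on it.** SpO2 is not a key secondary endpoint and has no estimand. Later p-values are nominal, and the proportions remain visible by arm. All of this stands and limits the weight of the point. It does not supply an estimate with an interval.

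**The size rests on assumptions.** This is true. The 5% figure needs a constant odds ratio. Under a constant percentage-point gain Breslow-Day does have power, though less than CMH in each such scenario, and a rejection still says nothing about direction. The no-net-change case needs opposite effects by baseline, which nothing in the documents suggests. It shows what the test responds to and is not a forecast.

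**Hochberg is a separate matter.** Agreed. It concerns all three endpoints listed in SAP 5.1, and the finding does not rest on it.

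**Conclusion.** The concern holds. The only planned between-arm test for Day-5 SpO2 ≥95% is a test of interaction under either reading, and no treatment odds ratio, interval or valid treatment p-value is planned. That conclusion follows from the definition of the test and needs no assumed rates.

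The numerical size does need them. With 940 evaluable participants per arm, a common odds ratio of 1.5 to 3 is rejected at about the 5% level by Breslow-Day, against 49% to 100% for a stratified treatment test. Participants with missing Day-1 or Day-5 values are excluded, so the real numbers will be smaller.

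This should be fixed, but it does not threaten the trial's main conclusions: the endpoint is a lower-ranked secondary, p-values are nominal, and descriptive proportions are kept.

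**What to change.** In SAP 5.2.3, 6.2.11 and Appendix 1, name one treatment comparison for Day-5 SpO2 ≥95%: either CMH stratified by Day-1 category, or logistic regression with treatment and Day-1 SpO2. The logistic option follows protocol 9.3.1 most closely; the Day-1 term goes beyond the treatment term named there and should be stated. Report the common odds ratio with its 95% interval and a nominal p-value. Keep Breslow-Day, if wanted, as a homogeneity check labelled as such.

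Separately, reconcile the Hochberg step with the nominal-testing statements. Protocol 9.1 says the other secondary endpoints "will be subsequently tested following the Hochberg procedure", while the protocol synopsis says "there is no remaining alpha for subsequent hypothesis tests". Either delete the step there and in SAP 5.1, or state that it is descriptive and carries no type I error claim.

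The cost is SAP wording in three places, one changed procedure call, and one sentence on Hochberg in each document. Because three interim analyses are already complete, the change should be recorded as a late one in the SAP version history. No data collection changes.

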6.2.12. PF-07321332 Plasma PK in Plasma and Whole Blood (if feasible)

The PK analysis will be performed and summarized descriptively by GPD Clinical Pharmacology. PF-07321332/ritonavir plasma and blood (if feasible) PK concentrations will be descriptively summarized for each time point and treatment group.

6.2.13. Viral Titers (quantitative RT-PCR) Measured in Nasal Swabs Over Time

The viral load data measured at Day 1 and Day 5 are nasopharyngeal samples. These are the samples that were used on the POC analysis. POC analysis of viral load data occurred when 25% (approximately 200 participants in the primary analysis set with evaluable data) in the mITT1 population with evaluable data complete the Day 5 assessments.

Descriptive statistics by treatment group for the change from baseline will be provided. An analysis of covariance (ANCOVA) model will be used to analyze the change from baseline in log base10 transformed viral load (copies/mL) data. The ANCOVA model will include treatment group, baseline viral load, baseline serology, geographical region and vaccination status. Symptom onset to first dose date (≤ 3 days, > 3 days) will be used in the model dependent of population. Participants are excluded from the analysis for reasons of Not Detected, Zero or Missing baseline viral load result. Results from samples collected at non-nasopharyngeal site (like nostril, other or missing) are also excluded, as well as exclusions due to non-validated swab use (only viral load data based on samples collected through validated swab will be used for analyses).

The viral load measured in nasal or nasopharyngeal samples over time will be evaluated. The change from baseline to each visit (Day 3, Day 5, Day 10, Day 14) in viral load will be analyzed using an MMRM method. Viral load, including change from baseline, will be summarized by treatment group. Change from baseline to Day 3/Day 5/Day 10/Day 14 in viral load in the log base 10 scale will be statistically analyzed using a linear mixed-effect model. The model will contain log base 10 transformed baseline as a covariate, baseline serology status, treatment, day, treatment-by-day as fixed effects. Symptom onset to first dose date (≤ 3 days, > 3 days), nasopharyngeal (Y/N) will be used in the model as described in Section 3.4 and 3.5, dependent of population. The LS means and treatment difference will be calculated and presented with their corresponding 95% CIs. The analyses will be done using mITT1 populations.

CCI [REDACTED]

CCI [REDACTED]

CCI [REDACTED]

CCI [REDACTED]

6.4. Subset Analyses

Subgroup analyses of the primary endpoint and key secondary endpoint (hospitalization due to COVID-19 and death of any cause) will only be performed for vaccination status and others will be analyzed if necessary for post hoc. The subgroup variables include:

- Age group (<65, ≥ 65);
- Sex;
- Race;
- Vaccination status. The vaccination subgroup is defined as follows:
 - a) Participant who enrolled prior to PA #5 and were completely vaccinated are considered high risk group.
 - b) Participants who enrolled prior to PA#5 and were not vaccinated, plus all participants enrolled after implementation of PA#5 are considered as standard risk group.
- Baseline serology (PCR positive, PCR negative);
- Baseline viral load defined as: <10⁴ copies/mL vs ≥10⁴ copies/mL;
- Maximum severity of targeted baseline signs and symptoms (mild, moderate, severe)
- Vaccination status and by maximum severity of targeted baseline signs and symptoms (mild, moderate, severe)
- Baseline viral load defined as: <10⁷ copies/mL vs ≥10⁷ copies/mL;
- BMI category (<30, ≥30);
- Type of COVID-19 variant (i.e., Omicron, BA2);
- Baseline Comorbidities:
 - Smoking;

- Chronic lung disease requiring medication;
- Hypertension (taking medications for hypertension);
- Cardiovascular disorders;
- Diabetes (taking medications for diabetes) for safety reporting;
- Chronic kidney disease;
- Sickle cell disease;
- Neurodevelopmental disorders;
- Cancer other than localized skin cancer;
- Medical-related technological dependence.

